5 MEDICAL DEVICE INFORMATION

5.1 Identity and Description of the Investigational Medical Device (IMD)

5.1.1 Kanso 2 and Kanso 2 NF Sound Processor

The Kanso 2 (CP1150) Sound Processor is the latest commercially available OTE Sound Processor from Cochlear Limited and provides an alternative form factor with similar functionality to current BTE Sound Processors. Functionality of the is enabled by the NEO-XS processing chip, which is also used in the current, approved (Nucleus 7) BTE processor.

The Kanso 2 NF Sound Processor is identical to the Kanso 2 Sound Processor with the addition of notch filters at 978Hz, 1956Hz, 2934Hz, 3912Hz. The principal architectural difference between OTE processors such as the CP1150 and BTE Sound Processors from Cochlear is that the RF coil that supplies power and data to the internal implant is housed within the processor, rather than in a separate unit connected by a cable to a BTE processing unit. The CP1150 is smaller than the existing CP950 (Kanso) OTE Sound Processor and delivers additional functionality. The external appearance and internal layout of the CP1150 are shown in Figure 4 and Figure 5.

Clinical Investigation Plan: CLTD5818

The

Figure 4: External view of the Kanso 2 (CP1150) Sound Processor

Sound is detected by two microphones placed symmetrically on the outer surface of the processor and protected from dirt and debris by a replaceable microphone cover.

external processor is aligned with the internal implant receiver coil by a magnet, which is available in different strengths to accommodate varying user hair types and skin thicknesses. Standard axial magnets are available in seven strengths and imaging (I) diametric magnets, used with CI600-series

Clinical Investigation Plan: CLTD5818

implants, are available in six strengths to prevent magnets becoming a choking hazard for small children, the magnets are designed to be tamper resistant and can only be removed from the Sound Processors using a specialised tool.

Unlike the CP950 (Kanso) and CP1000 (Nucleus 7) devices, the CP1150 has no control button. The processor is turned on by double-tapping the Cochlear logo on the housing and turned off by triple-tapping. These functions are enabled by an accelerometer, which also enables the Auto On feature, detecting the "raise to wake" motion. Other controls can be accessed via the Nucleus Smart App on iOS and Android devices or the optional CR310 remote control.

5.1.2 CP1150 Sound Processor Accessories

5.1.2.1 CP1150 Programming Adaptor Cable

The programming adaptor cable (Figure 6) enables the Sound Processors to be programmed via a connection to either a Cochlear Wired Programming Pod or Cochlear Wireless Programming Pod interface.

The programming adaptor cable connects the Sound Processors directly to the PIF5.2 programming interface. Connection to the PIF4 interface is enabled by connecting the CP1150 programming adaptor cable to the CP1000 Programming Cable.

Figure 6: Kanso 2 (CP1150) programming adaptor cable

5.1.3 Additional Components

5.1.3.1 Compatible implants

The CP1150 Sound Processor must be used together with a compatible implanted receiverstimulator for normal operation. It is compatible with all CIC3 based implants and CIC4 based implants available in the market as listed below (Table 1). The CP1150 is not currently compatible with Nucleus 22 Series implants.

Clinical Investigation Plan: CLTD5818

Table 1 Internal implants compatible with the Kanso 2 NF Sound Processors

Family	Model	Electrode
CI600 (CIC4)	CI612	Contour Advance
	CI622	Slim Straight Half Band Electrode
	CI6241	Slim 20
	CI632	Slim Modiolar Electrode
CI500 (CIC4)	CI512	Contour Advance
	CI513	Contour LEAP
	CI522	Slim Straight Half Band Electrode
	CI532	Slim Modiolar Electrode
	CI551 ²	Double Array
	ABI541	ABI
CI24RE (CIC4)	CI24RE(CA)	Contour Advance
	CI24RE(ST)	Straight
	CI24REH	Hybrid L24
	CI24RES	Hybrid S8, Hybrid S12
	CI24RE(CS)	Contour Straight
	CI422	Slim Straight Half Band Electrode
Nucleus 24 (CIC3)	CI24R(CS)	Contour
	CI24R(CA)	Contour Advance
	CI24R(ST)	Straight
	CI24M	Straight
	ABI24M	ABI
	CI11+11+2M	Double Array
	CI24MH (CI6+16+2M)	Hybrid

¹not yet approved; ²not commercially available in Europe

5.1.3.2 CR310 Remote control

The CR310 Remote Control allows the user to perform basic control functions on the paired Sound Processor, including changing programs, adjusting loudness and selecting the audio source. The Remote Control supports data communication via the NEO-XS Proximity 2 protocol over a 2.4 GHz wireless link and is compatible with the Kanso 2 NF Sound Processors.

5.1.3.3 Programming interfaces

The Kanso 2 NF Sound Processor is compatible with the Cochlear Wired Programming Pod and the Cochlear Wireless Programming Pod.

The Kanso 2 NF Sound Processor is compatible with Custom Sound 6.1 or later, which operates on a computer running Windows OS. It is not compatible with Nucleus Fitting Software (NFS) or Custom Sound Electric Potential.

Clinical Investigation Plan: CLTD5818

5.2 Identity and Description of the Comparator

Kanso 2 (CP1150) Sound Processor:

Kanso (CP1150) Sound Processor is the commercially available predecessor device to the investigational Kanso 2 NF Sound Processor. Kanso 2 will be used as the comparator device for speech perception testing in quiet (CNC words) for both the NF and FF comparisons.

Nucleus 8 (CP1110) Sound Processor:

Nucleus 8 is an unapproved BTE Sound Processor. The Nucleus 8 is considered a suitable comparator for the OTE vs BTE comparison (secondary endpoint 2) because of the similarities to the commercially available predicate Nucleus 7 Sound Processor, and because Nucleus 8 includes signal processing features aligned with the next generation of OTE Sound Processor.

Comparator	Endpoint	Justification
Kanso 2 (CP1150) Sound Processor	Primary Endpoints Paired difference in percentage CNC Words correct in quiet (50 dB) with the Kanso 2 Sound Processor and Kanso 2 NF Sound Processor	Input processing: Standard microphone directionality + SNR-NR + subject's own MAP and ADRO/ASC preference Standard microphone directionality has been chosen to be consistent with the microphone directionality that SCAN+ selects in a quiet setting, and because the impact of the notch filters have the greatest potential for impact on speech in quiet.
Kanso 2 (CP1150) Sound Processor	Secondary Endpoints Paired difference in percentage CNC Words correct in quiet (50 dB) with the Kanso 2 Sound Processor and Kanso 2 Sound Processor with FF	Input processing: Standard microphone directionality + SNR-NR + subject's own MAP and Adaptive Dynamic Range Optimisation Autosensitivity (ADRO/ASC) preference Standard microphone directionality has been chosen to be consistent with the microphone directionality that SCAN+ selects in a quiet setting, and because the research question includes the performance of FF in a quiet scenario.
Nucleus 8 (CP1110) Sound Processor	Secondary Endpoints Paired difference in percentage CNC Words correct in quiet (50 dB) with the Kanso 2 Sound Processor and Nucleus 8 Sound Processor	Input processing: Standard microphone directionality + SNR-NR + subject's own MAP and ADRO/ASC preference Standard microphone directionality has been chosen to be consistent with the microphone directionality that SCAN+ selects in a quiet setting
Kanso 2	Exploratory Endpoint Paired difference in percentage phonemes correct in quiet (50 dB) with the Kanso 2 Sound Processor and Kanso 2 NF Sound Processor NF	See primary endpoint justification

Table 2. Comparator conditions

Clinical Investigation Plan: CLTD5818

5.3 Accessory Device Requirements

Nucleus 8 Sound Processor

The Nucleus 8 SP must be used together with an implanted receiver-stimulator to achieve normal operation in clinical use.

To utilise the Sound Processor system, in addition to the processing unit, recipients will also use a compatible ear hook, battery module, coil, and magnet.

The Nucleus 8 Sound Processor is compatible with the Cochlear™ Wired Programming Pod.

Kanso 2 and Kanso 2 NF Sound Processors

The Kanso 2 Sound Processor and the Kanso 2 NF Sound Processor must be used together with an implanted receiver-stimulator to achieve normal operation in clinical use. The Kanso 2 Sound Processor and Kanso 2 NF Sound Processors NF are not currently compatible with the Nucleus 22 Series implants. For the current study, the implants in Table 2 will be used.

All study Sound Processors will be compatible with the Custom Sound Pro fitting software. This software will be used by the investigator to program the Sound Processors.

The research signal processing configurations will be programmed via CDI-Tool Version 7.3.1.

6 **OBJECTIVES**

6.1 Primary Objective

To evaluate the impact of NF on adult cochlear implant recipient's speech perception in quiet using an off-the-ear (OTE) Sound Processor.

6.2 Secondary Objectives

- To evaluate the performance of FF combined with standard microphone directionality on adult cochlear implant recipient's speech perception in quiet using an OTE Sound Processor.
- To compare adult cochlear implant recipient's speech perception in quiet with Kanso 2 and Nucleus 8 Sound Processors

6.3 Exploratory Objective

To characterise the impact of NF on adult cochlear implant receipients, phoneme perception in quiet using an OTE (Kanso 2) Sound Processor.

7 DESIGN OF THE CLINICAL INVESTIGATION

7.1 General

This is a pre-marketing, prospective, single-site, open-label, within-subject, pilot, interventional clinical investigation in adults with sensorineural hearing impairment who are current users of a Nucleus Cochlear Implant system.

Clinical Investigation Plan: CLTD5818

See section 7.2 for description of subject population.

After enrolment, subjects will attend a single study visit as described in the CIP Schedule of Events (Section 3). At the study visit, subjects will undergo hearing assessments. Safety will be assessed by recording and summarising all Adverse Events (AE)/ Adverse Device Effects (ADE) and Device Deficiencies (DD). No data monitoring committee will be used for this clinical investigation.

7.1.1 Design Rationale

Experienced adult cochlear implant recipients have been chosen as the study population due to their ability to compare Sound Processors across generations, in and outside of the booth. In addition, performance benefits achieved by adults can generally be extrapolated to younger age groups, avoiding the need to recruit this vulnerable population.

Comparison will be made within subjects with repeated measures for each of the sound processing conditions to be evaluated. There will be two test sessions with no take home use between sessions. The test sessions will include words in quiet tests. These speech measures are routine outcome measures used to evaluate new signal processing algorithms and hardware.

There will be no blinding of the study investigators.

Blinding of the study subject will be undertaken where possible, particularly when multiple signal processing conditions are loaded onto a single study device. Patients will not be told which program will be used in which order, and because the Kanso 2, Kanso 2 NF and Kanso 2 FF Sound Processors are physically identical, it may also be possible to conceal which Sound Processor is being used during testing.

Counterbalancing of the test order will be undertaken where possible to limit the influence of order effects on results.

7.2 Subjects

The subjects include men and women aged 18 years or older who are current users of a Nucleus 6 (CP910/920), Kanso 2 (CP1150), Kanso (CP950) or Nucleus 7 (CP1000) Sound Processor. Subjects will be screened, and 20 eligible subjects will be recruited to the clinical investigation. For speech perception testing, all subjects will receive all treatment and control conditions; however, the test order will be counterbalanced to control for order effects.

Written, informed consent must be obtained from the subject before any study procedures are initiated.

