7.2.3 Number of Subjects Required

The total number of subjects to be enrolled in the study to meet sample size calculation requirements is 12, which includes 3 additional subjects to account for an expected dropout rate of 25%.

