9.4 Sample Size Determination

This study is a non-inferiority design, and sample size calculation was based on non-inferiority tests for CNC word scores. The sample size using a confidence interval method (two-tailed 95% confidence interval) was estimated to have a reasonable power to detect non-inferiority word scores for the listed hypotheses.

To reject the null hypothesis of inferior word perception in quiet for the New processor:

- A margin of non-inferiority of 10% (new-old) has been chosen. That is saying that a true mean difference of anything up to 10% is acceptable and not clinically meaningful. This margin is based on clinical consensus, and previous feedback from the FDA
- An expected standard deviation of difference scores of 7.5% for CNC words (50 dB), based on previous OTE studies investigating words in quiet.
- A significance level $\alpha = 0.05$ (two-tailed).
- A desired power of 0.9.

Based on these assumptions, a sample size of 9 subjects is required to reject the null hypothesis. An increased sample size of 12 subjects will be enrolled, which will allow for the possibility that the variability in difference scores will be greater than expected and to account for the possibility of subject attrition.

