## **5 ANALYSIS POPULATIONS**

This study has a non-inferiority design; therefore, the primary analysis will be based on the PP population. If non-inferiority is demonstrated, the test of superiority in the Per Protocol (PP) and the Intent-To-Treat (ITT) analysis sets will follow.

For cases in which the ITT and PP populations lead to the same conclusions and final interpretations about the treatment effect, the results will be considered to not be influenced by underlying factors such as missing data and protocol deviations, and the results would be considered to be robust and consistent under different analysis populations. A statement to reflect this will be included in the CIR.

For cases in which the ITT and PP populations lead to different final interpretations or conclusions, the results will be reported for both analysis sets and the differences in outcomes will be identified and explored.

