### **5.2 Per Protocol Analysis Set**

The Per Protocol Population will include all subjects who receive the treatments and have at least one paired measurement from treatment and control, without major protocol deviations. Major deviations will be defined at the clean file meeting before data base lock.

It is possible that a treatment has not been administered in the intended counterbalanced order of presentation.

It is also expected that the sequence and period effects are likely to be negligible in this study.

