### **5.6 Protocol Deviations**

Major protocol deviations will be listed for the safety population with the reason(s) for the deviation(s). Major deviations will include violations of eligibility criteria, incorrect order of administration of the SPs, or an incorrect administration of a test condition.

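### Protocol section 7.2 recruits 20 eligible subjects, but the sample-size sections of the protocol and SAP justify and enrol 12, and Table 3 lists test orders for 12 only

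*Protocol*

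**What the plan says.** Protocol section 7.2 (Subjects): "Subjects will be screened, and 20 eligible subjects will be recruited to the clinical investigation". The next sentence gives every subject all conditions and adds that "the test order will be counterbalanced to control for order effects".

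The other places that give a number are:

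- Protocol section 7.2.3: the total to be enrolled "is 12, which includes 3 additional subjects to account for an expected dropout rate of 25" per cent.
- Protocol section 9.4: "a sample size of 9 subjects is required to reject the null hypothesis", then "An increased sample size of 12 subjects will be enrolled". SAP section 1.3 gives the same two figures.
- Protocol synopsis, number of subjects planned: 9 to 12.
- Table 3 (protocol section 7.2.7 and SAP section 1.4): a four-row balanced Latin square with three subject numbers per row, ending at SYD12.

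The figure 20 appears nowhere else as a number of subjects.

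**The concern.** The number of subjects to recruit is a core parameter. The ethics committee reviews it and the site works to it. Here one protocol gives two numbers that cannot both be met. A site that follows section 7.2 exceeds the total in section 7.2.3, and a site that stops at 12 falls short of section 7.2.

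What is at stake is limited but real. Eight people beyond the justified total would be asked to take part in a study that, by protocol section 8.1, offers subjects no long-term benefit. Table 3 as printed gives no test order for them.

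**Working it through.** **1. Can the two numbers be reconciled by reading?**

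- The 20 is not a number to screen. The sentence mentions screening first and then gives 20 as eligible subjects recruited.
- Protocol section 7.2.5 defines an enrolled subject as one who has signed consent, so enrolment includes screen failures. A total of 12 enrolled cannot contain 20 eligible subjects.
- The 20 is not an allowance for replacements. Protocol section 7.2.6 says that withdrawn participating subjects are not replaced.

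**2. Does the stated 9 reproduce?**

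Inputs from protocol sections 9.4 and 9.6: margin 10 points, SD of paired differences 7.5 points, one-sided alpha 0.025 (two-sided 95% interval), power 0.9. The documents do not state a true difference, so d = 0 is assumed.

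Power of the paired non-inferiority t-test = 1 − F(t[0.975, n−1]), where F is the non-central t distribution on n−1 degrees of freedom with non-centrality (10 + d)·√n / 7.5.

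- n = 8: non-centrality 10 × 2.828 / 7.5 = 3.77; power 89.6%.
- n = 9: non-centrality 10 × 3 / 7.5 = 4.00; power 93.7%.

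The smallest n with at least 90% power is 9, as stated. The normal approximation, (7.5 × (1.960 + 1.282) / 10)² = 5.91, would give 6, so the plan's figure matches the t-based method.

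**3. Does the stated 12 reproduce?**

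9 / (1 − 0.25) = 12, and 12 − 9 = 3 additional subjects, as in section 7.2.3. Table 3 agrees: 4 orders × 3 subjects = 12.

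**4. Does 20 follow from anything stated?**

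- 20 × 0.75 = 15, so 20 recruited would correspond to 15 evaluable. The plan requires 9.
- 12 / 20 = 0.60, so inflating 12 to 20 needs 40% dropout. The plan states 25%.

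Neither input is in the documents.

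**5. Size of the discrepancy**

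20 − 12 = 8 extra subjects; 8/12 = 67% more.

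| Evaluable n | Power, d = 0 | Power, d = −2 | Power, d = 0 but SD 10 |
|---|---|---|---|
| 9 | 93.7% | 80.0% | 74.8% |
| 12 | 98.7% | 91.9% | 88.3% |
| 15 | 99.8% | 97.0% | 94.9% |
| 20 | 99.99% | 99.5% | 98.9% |

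The last two columns show how the result moves if the assumed difference or the SD is less favourable. In every column power rises with n, so recruiting 20 would cost subjects and not power.

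**The case against.** The strongest reply is that this is one stray number in an introductory paragraph. The section headed with the number of subjects required, both sample-size sections and both copies of Table 3 agree on 12, the synopsis range ends at 12, and the SAP never mentions 20. No endpoint, error rate or decision rule depends on it. All of that stands, and it shows which figure the plan supports. It does not make section 7.2 correct: that sentence is current text and states a recruitment target.

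One could also say that more subjects guard against a larger SD, as the table shows. But protocol section 9.4 already gives extra variability as a reason for going from 9 to 12, and offers no such reason for 20.

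Three stronger readings may tempt a reader, and the documents do not support them.

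- **That the design cannot be run with 20.** Table 3 as printed is incomplete for 20, but its rows repeat every four subject numbers and 20 = 4 × 5, so the same square extends directly. Protocol section 7.1.1 also promises counterbalancing only where possible.
- **That subjects 13 to 20 would drop out of the primary analysis.** SAP section 5.6 says "Major deviations will include violations of eligibility criteria, incorrect order of administration of the SPs", SAP section 5.2 admits to the per-protocol set subjects "without major protocol deviations", and SAP section 5 says "the primary analysis will be based on the PP population". But section 5.6 concerns a wrong order, not an unlisted one, and SAP section 5.2 leaves the definition of major deviations to the clean file meeting before database lock. Loss from the primary set is speculation.
- **That the contradiction turns on screen failures.** Whether they count towards the 12 enrolled is a separate missing detail. It need not be settled to resolve 20 against 12.

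**Conclusion.** Protocol section 7.2 is wrong as written. Its 20 contradicts the 12 enrolled in protocol sections 7.2.3 and 9.4 and SAP section 1.3, the 9 to 12 of the synopsis, and the 12 subject numbers in Table 3. The excess is 8 subjects, or 67%.

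The contradiction itself rests on no assumption. The check that the stated inputs lead to 9 and then 12 assumes a true difference of 0. With SD 7.5, 9 is the smallest adequate n for true differences from about −0.7 to +0.06 points. The sample-size calculation is sound on that assumption. The claim about 20 is only that neither document derives it, not that no inputs could.

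The consequence is a recruitment target in conflict with its own justification. It is not a loss of power, a change in the analysis or a threat to the non-inferiority conclusion.

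**What to change.** In protocol section 7.2, change the number of eligible subjects from 20 to 12. In the synopsis, replace the 9 to 12 range with 12, noting that 9 evaluable are required.

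If the sponsor does intend 20, change protocol sections 7.2.3 and 9.4, the synopsis, SAP section 1.3 and both copies of Table 3 instead, and state the inputs that produce 20.

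Keeping 12 costs a wording amendment to the protocol, with notification to the ethics committee under protocol section 18. SAP section 1.3 and Table 3 need no change, and the analysis is untouched.

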7.2.1 Inclusion Criteria

Subjects must meet all of the inclusion criteria described below to be eligible for this clinical investigation.

- 1) Aged 18 years or older
- 2) Post lingually deafened
- 3) Implanted with the CI600 Series, CI500 Series or Freedom Series
- 4) At least 6 months experience with a cochlear implant.

Clinical Investigation Plan: CLTD5818

- 5) At least 3 months experience with a Nucleus 6 (CP910/920), Kanso (CP950), Kanso 2 (CP1150), or Nucleus 7 (CP1000) Sound Processor
- 6) MAP Total Stimulation Rate of 7.2kHz or greater
- 7) Able to score 30% or more with CI alone on a monosyllabic word in quiet test
- 8) Willingness to participate in and to comply with all requirements of the protocol
- 9) Fluent speaker in English as determined by the investigator
- 10) Willing and able to provide written informed consent

7.2.2 Exclusion Criteria

Subjects who meet any of the exclusion criteria described below will not be eligible for this clinical investigation.

- 1) Additional disabilities that would prevent participation in evaluations.
- 2) Implant location that would result in undesirable hearing performance or discomfort with an off-the-ear Sound Processor, as determined by the investigator.
- 3) Unable or unwilling to comply with the requirements of the clinical investigation, as determined by the Investigator.
- 4) Investigator site personnel directly affiliated with this study and/or their immediate families; immediate family is defined as a spouse, parent, child, or sibling.
- 5) Cochlear employees or employees of Contract Research Organisations or contractors engaged by Cochlear for the purposes of this investigation.
- 6) Currently participating or participated in another interventional clinical study/trial in the past 30 days unless (if less than 30 days) the prior investigation was Cochlear sponsored and determined by the investigator to not impact clinical findings of this investigation.
- 7) Implanted with other active implantable medical devices (e.g., pacemaker, defibrillator).

